## **4.0 OBJECTIVES**

### **4.1 Primary Objective**

To characterize the effect of a high-fat meal on the pharmacokinetics (PK) of mobocertinib (referred to as TAK-788 in the protocol) administered as a proposed commercial product.

### **4.2 Secondary Objective**

To assess the PK of active metabolites AP32960 and AP32914 of mobocertinib.

### **4.3 Exploratory Safety Objective**

To collect the safety data of mobocertinib following a single oral dose in healthy adult subjects.

### **4.4 Study Design**

This is an open-label, randomized, 2-period, and 2-sequence crossover high-fat meal effect study in healthy adult subjects.

Subjects will undergo screening evaluations to determine eligibility within 21 days prior to dosing. Subjects will be admitted to the clinical facility the day prior to dosing in each period (Day -1). Subjects will be randomized on Day 1 of Period 1 to a crossover sequence in a 1:1 ratio and administered a single oral dose of 160 mg of mobocertinib with or without a high-fat meal on Day 1 of each period (i.e., Period 1 and Period 2). Each dose will be separated by a washout period of 10 days. Blood samples for mobocertinib PK will be collected predose and up to 240 hours following each mobocertinib dose.

Subjects will receive the following treatments on one occasion in a crossover fashion to evaluate the effect of a high-fat meal:

- Treatment A: Administration of a single oral dose of 160 mg mobocertinib (4 x 40 mg capsules) following an overnight fast.
- Treatment B: Administration of a single oral dose of 160 mg mobocertinib (4 x 40 mg capsules) with a high-fat meal.

\* 800-1000 total calories, 500-600 calories, 55-65 g, or 50% from fat

Subjects will remain at the clinical site until the 240-hour study assessments in Period 2 are completed. All doses of mobocertinib will be administered at the clinic during this study. A final safety follow-up phone call will occur  $30 \pm 2$  days after the last mobocertinib dose to determine if any adverse events (AEs) have occurred since the last study visit. Replacement of discontinued or withdrawn subjects due to any reason will be assessed on a case by case basis by the Sponsor and the Principal Investigator (PI) to ensure a minimum of 12 PK-evaluable subjects complete the study.

Any subject who experiences emesis within 8 hours postdose will be excluded in the final PK data analysis and may be replaced with a new subject.

## **5.0 ANALYSIS ENDPOINTS**

### **5.1 Primary Endpoints**

The following PK parameters will be analyzed for mobocertinib:

- Time of first occurrence of  $C_{\max}$  ( $t_{\max}$ ).
- Maximum observed concentration ( $C_{\max}$ ).
- Area under the concentration-time curve from time 0 to infinity, calculated using the observed value of the last quantifiable concentration ( $AUC_{\infty}$ ).
- Area under the concentration-time curve from time 0 to the time of the last quantifiable concentration ( $AUC_{\text{last}}$ ).

### **5.2 Secondary Endpoints**

The following PK parameters will be analyzed for active metabolites (AP32960 and AP32914) of mobocertinib:

- Time of first occurrence of  $C_{\max}$  ( $t_{\max}$ ).
- Maximum observed concentration ( $C_{\max}$ ).
- Area under the concentration-time curve from time 0 to infinity, calculated using the observed value of the last quantifiable concentration ( $AUC_{\infty}$ ).
- Area under the concentration-time curve from time 0 to the time of the last quantifiable concentration ( $AUC_{\text{last}}$ ).

### **5.3 Exploratory Safety Endpoints**

The exploratory endpoint will be assessed through evaluation of the following safety parameters:

- Treatment-emergent adverse events (TEAEs) assessments.
- Clinical laboratory (hematology, serum chemistry, and urinalysis).
- Physical examinations.
- 12-lead electrocardiograms (ECGs).
- Vital signs.

## **5.4 Additional Endpoints**

In addition, the following plasma PK parameters for mobocertinib and its active metabolites (AP32960 and AP32914) will be calculated:

- Terminal disposition phase half-life ( $t_{1/2z}$ ).
- Terminal disposition phase rate constant ( $\lambda_z$ ).
- Percent of  $AUC_{\infty}$  extrapolated
- Apparent clearance after extravascular administration (CL/F) for mobocertinib only.
- Apparent volume of distribution during the terminal disposition phase after extravascular administration ( $V_z/F$ ) for mobocertinib only.
- The metabolite to parent ratio for molar  $AUC_{\infty}$  (MPR  $AUC_{\infty}$ ) for AP32960 and AP32914.

## **6.0 DETERMINATION OF SAMPLE SIZE**

The sample size calculation was based on the expected 2-sided 90% confidence interval (CI) for the difference in the paired, log-transformed  $AUC_{\infty}$  means of mobocertinib in the presence and absence of a high-fat meal. The within-patient coefficient of variation for mobocertinib  $C_{\max}$  was estimated to be 17.2% on the basis of data from a clinical study conducted in healthy subjects (TAK-788-1001). If the observed geometric mean ratio (GMR) for the mobocertinib  $AUC_{\infty}$  in the presence and absence of high-fat is 1, with a sample size of 12, the 90% CI for the  $AUC_{\infty}$  GMR is expected to be 0.881 to 1.13 on the basis of the variance assumptions. Fourteen (14) adult subjects will be enrolled into this high-fat meal effect study to get at least 12 PK-evaluable subjects in each treatment according to the Food and Drug Administration (FDA) guidance Assessing the Effects of Food on Drugs in Investigational New Drugs (INDs) and New Drug Applications (NDAs) – Clinical Pharmacology Considerations Guidance for Industry (FDA food effect [FE] 2019).

## **7.0 METHODS OF ANALYSIS AND PRESENTATION**

### **7.1 General Principles**

All PK analyses will be conducted using Phoenix® WinNonlin® Version 8.1, or higher. All statistical analyses will be conducted using SAS® Version 9.4, or higher. All data recorded on the case report form (CRF) will be listed by subject. All tables, figures, and listings (TFLs) shells and numbering list will be included.

The concentration data will be used as reported by the respective bioanalytical groups without rounding for all analyses. Concentration values below the limit of quantitation (BLQ) will be presented as 'BLQ' in the concentration table listings and footnoted accordingly. BLQ values will be treated as zero for the calculation of summary statistics, the generation of concentration plots, and the calculation of PK parameters, unless they are obvious outliers (e.g. BLQ value between 2 measurable values [except in cases where more than 2 samples are BLQ between measurable concentrations, BLQ values will be set to 0 instead of missing]), in which case they will be treated as missing. In log-linear plots, these values would not be presented. Missing concentration values will be flagged in the concentration tables and footnoted as missing or not reportable (i.e., for subjects withdrawn or dropped from the study, subjects missing blood draws). Plasma concentration data from subjects excluded from PK parameter analysis will be included in the concentration tables and individual figures, but will be excluded from summary statistics and in the presentation of mean figures.

All concentration and PK parameter values will be presented to 3 significant figures. For concentration and PK parameter tables, all summary statistics will be presented to 3 significant figures. Geometric least-squares means (LSMs) will be presented with 3 significant figures. GMRs and 90% CIs around the ratio will be reported using 2 decimal places.

For the calculation of PK parameters, if actual times are missing, nominal times will be used instead.

A subject's PK parameter data will be included in the listings but excluded from the descriptive statistics and statistical evaluation if one or more of the following criteria are met:

- A predose (0 hr) concentration is greater than 5% of that subject's Cmax value in that period
- A subject did not meet inclusion/exclusion criteria that may have an effect on the PK (as determined by the Takeda Clinical Pharmacology Lead and Celerion Pharmacokinetic Scientist)
- A subject deviates substantially from the protocol defined study procedures including but not limited to dosing, dose timing, sample collection, meal timing/consumption, etc. (as determined by the Takeda Clinical Pharmacology Lead and Celerion Pharmacokinetic Scientist)

See CPAP for details on the PK parameter calculations and data presentation including specifics on the following:

- Insufficient data to determine a reliable  $t_{1/2z}$  value and other terminal elimination rate constant dependent parameters
- PK parameters presented by treatment, including the units, precision, and summary statistics that will be presented in in-text and end of text tables
- Concentration data presented by treatment, including the units, precision, and summary statistics that will be presented in end-of-text tables
- Concentration data file used for PK analysis
- PK parameter WinNonlin® output file used to generate the TFLs
- Analysis of variance (ANOVA) results presented in in-text and end of text tables
- Arithmetic mean concentration-time figures presented as in-text and end-of-text figures
- Individual concentration-time figures presented in Appendix 16.2.6
- Any subject, PK concentration, and PK parameter that are excluded in the PK data analyses or summary statistical analyses will be provided in end of text tables.

For demographic data where appropriate, variables will be summarized descriptively. For the categorical variables, the count and proportions of each possible value will be tabulated, where applicable. The denominator for the proportion will be based on the number of subjects who provided non-missing responses to the categorical variable. For appropriate continuous variables, the number of subjects with non-missing values, mean, standard deviation (SD), minimum, median, and maximum values will be tabulated.

## **7.1.1 Study Definitions**

### **7.1.1.1 Definition of Study Days**

Day 1 for each period is defined as the date on which a subject is administered their first dose of the study drug in each period. Other study days are defined relative to Day 1 with Day -1 being the day prior to Day 1 of each period. Study day prior to the first dose of each treatment will be calculated as: date of assessment-date of first dose in each period; study day on or after the date of first dose will be calculated as: date of assessment-date of first dose in each period +1.

For all clinical laboratory evaluations, vital signs, and 12-lead ECGs, baseline is defined as the last assessment including rechecks taken prior to mobocertinib dosing at each period.

## **7.2 Analysis Sets**

PK Set:

Samples from all subjects will be assayed even if the subjects do not complete the study. All subjects who comply sufficiently with the protocol and display an evaluable PK profile (eg, exposure to treatment, availability of measurements and absence of major protocol violations) will be included in the statistical analyses. Any subject who experiences emesis within 8 hours post dosing with mobocertinib will be excluded in the final data analysis.

Safety Set:

All subjects who received at least one dose of a study drug will be included in the safety evaluations.

## **7.3 Study Information**

A study information table will be generated including the following items: date of first subject's signed informed consent form (ICF), date of first dose, date of last dose, date of last subject's last visit/contact, date of last subject's last procedure for collection of data for primary endpoint, the version of Medical Dictionary for Regulatory Activities (MedDRA®), the version of World Health Organization (WHO) Dictionary, and SAS version used for creating the datasets.

## **7.4 Disposition of Subjects**

Disposition of subjects (number of subjects dosed, completed the study, discontinued from the study, and reason(s) for discontinuation) will be summarized by randomized treatment sequence and overall. Study completion status, including reason for discontinuation, will also be listed by subject.

## **7.5 Demographic and Other Baseline Characteristics**

Demographic and baseline characteristics will be summarized descriptively by randomized treatment sequence and overall. Summary statistics (number of subjects [n], mean, SD, minimum, median, and maximum) will be generated for continuous variables (age [recorded in the CRF], weight, height and body mass index [BMI]) and the number and percentage of subjects within each category will be presented for categorical variables (sex, race, and ethnicity). Height, weight, and BMI recorded at screening will be used in the baseline summaries. Demographics data will also be listed as recorded on the CRF, including the date of informed consent.

## **7.6 Medical History and Concurrent Medical Conditions**

Medical history to be obtained will include determining whether the subject has any significant conditions or diseases relevant to the disease under study that resolved at or before signing the ICF. Concurrent medical conditions are those significant ongoing conditions or diseases that are present at signing the ICF. Each subject's medical history and concurrent medical conditions will

be listed. Any medical condition started after taking the study drug will be classified as an adverse event. All medical history will be coded using the Medical Dictionary for Regulatory Activities (MedDRA®), as described in the Data Management Plan (DMP). The medical history listing will include whether the event was medical or surgical, the body system or organ class involved, coded term, start date (if known) and end date or whether the condition was ongoing, and a description of the condition or event. There will be no statistical analysis of medical history.

## **7.7 Medication History and Concomitant Medications**

Medication history to be obtained includes any medication relevant to eligibility criteria and safety evaluation stopped at or within 28 days prior to signing the ICF. Concomitant medication includes any medication other than study drug taken at any time between time of signing the ICF through the end of the study (including follow-up visit). All medication history and concomitant medications recorded during the study will be coded with the MedDRA® Version 23.0, as described in the DMP, and listed. If appropriate, the listing will include the medication name, coded term, dosage, route of administration, start date and time (if known), end date and time, or whether it continued after study completion, and indication for use.

## **7.8 Study Drug Exposure and Compliance**

The date, time, and dosage of each mobocertinib dose along with meal data will be listed by subject.

## **7.9 Efficacy Analysis**

Not applicable.

## **7.10 Pharmacokinetic/Pharmacodynamic Analysis**

### **7.10.1 Pharmacokinetic Analysis**

Blood samples for PK analysis of mobocertinib, AP32960, and AP32914 will be collected as specified in Table 7:1 following administration of mobocertinib under fasted conditions (Treatment A) or with a high-fat meal (Treatment B).

**Table 7:1 Collection of Blood Samples for Pharmacokinetic Analysis**

Analyte	Matrix	Sampling Day	Period	Scheduled Time (hours)
mobocertinib, AP32960, and AP32914	Plasma	1	1 and 2	Predose and 0.5, 1, 2, 4, 6, 8, 12, 24, 48, 72, 120, 168, and 240 hours postdose (a) (b)

(a) If a subject experiences a serious adverse event (SAE), a blood sample for PK analysis should also be obtained at the unscheduled visit. PK samples will be collected at Early Termination at the discretion of the PI.

(b) The Period 1 Day 11 PK sample will serve as the pre-dose PK sample for Period 2.

The actual date and time of sample collection will be recorded on the source document in the CRF.

Concentrations will be listed and summarized descriptively by PK sampling time in mass units for plasma mobocertinib, AP32960, and AP32914. Summary will be done by treatment using the summary statistics listed in the CPAP. Excluded concentrations will be presented and footnoted as such in the concentration table listings, and those values will be excluded from the descriptive summary statistics. Individual subject and arithmetic mean profiles of the concentration-time data will be plotted by treatment on linear (with and without SD) and semi-log scales in mass units for each analyte. For summary statistics and arithmetic mean plots by sampling time, the nominal PK sampling time will be used, for individual subject plots by time, the actual PK sampling time will be used.

The PK parameters of mobocertinib, AP32960, and AP32914 listed in the CPAP for this study will be determined from the concentration-time profiles for subjects in the PK set using a noncompartmental analysis method in mass units. The molar  $AUC_{last}$ ,  $AUC_{\infty}$ , and  $C_{max}$  PK parameters will also be calculated for plasma mobocertinib, AP32960, and AP32914 using the molecular weights of each analyte as outlined in the CPAP. Combined molar  $AUC_{last}$ ,  $AUC_{\infty}$ , and  $C_{max}$  for plasma mobocertinib, AP32960, and AP32914 will also be presented. Actual sampling times, rather than scheduled sampling times, will be used in all computations involving sampling times. If actual sample times are missing, nominal times may be used.

PK parameters will be summarized descriptively by treatment using the summary statistics listed in the CPAP in mass units and molar units. Excluded parameters will be presented and footnoted as such in the PK parameter table listings, and those values will be excluded from the descriptive summary statistics.

### **Food Effect**

For evaluation of potential effect of a high-fat meal on mobocertinib PK, a linear mixed-effects model will be used for the analysis on the ln-transformed  $C_{max}$ ,  $AUC_{\infty}$ , and  $AUC_{last}$  (only if  $AUC_{\infty}$  is not available for at least 12 subjects) for mobocertinib (mass units) and combined molar  $C_{max}$ ,  $AUC_{\infty}$ , and  $AUC_{last}$  (only if  $AUC_{\infty}$  is not available for at least 12 subjects) for mobocertinib, AP3260, and AP32914. The mixed effects models will include sequence, treatment, and period as fixed effects, and subject nested within sequence as a random effect. Each model will include calculation of LSMS as well as the difference between LSMS.

GMR and 90% CIs, consistent with the two one-sided tests, will be calculated using the exponentiation of the difference between treatment LSMS from the analyses on the ln-transformed  $C_{max}$ ,  $AUC_{\infty}$ , and  $AUC_{last}$  (only if  $AUC_{\infty}$  is not available for at least 12 subjects) for mobocertinib, as well as the ln-transformed molar combined  $C_{max}$ ,  $AUC_{\infty}$ , and  $AUC_{last}$  (only if  $AUC_{\infty}$  is not available for at least 12 subjects) for mobocertinib, AP32960, and AP32914. The comparison of interest is as follows:

Treatment B (High-Fat Meal) relative to Treatment A (Fasted)

The following SAS code will be used:

```
PROC MIXED DATA=XXXX;  
CLASS Treatment Subject Period Sequence;  
MODEL <PK_Parameter> = Treatment Period Sequence / DDFM=KR;  
RANDOM Subject(Sequence);  
ESTIMATE 'Treatment B vs A' Treatment -1 1 / CL ALPHA = 0.10 E;  
LSMEANS Treatment;  
Run;
```

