A linear mixed-effects model will be used for the analysis on the natural log (ln)-transformed C_{\max} , AUC_{∞} , and AUC_{last} for TAK-788 and its active metabolites (AP32960 and AP32914). The model will include sequence, treatment, and period as a fixed-effect and subject nested within sequence as a random-effect. Each model will include calculation of least squares means (LSMs) as well as the difference between treatment LSMs.

Geometric mean ratios (GMR) and 90% confidence intervals (CI), consistent with the two one sided test [Schuirmann 1987], will be calculated using the exponentiation of the difference between treatment LSMs from the analyses on the ln-transformed C_{\max} , AUC_{∞} , and AUC_{last} (if it is needed) for TAK-788 and the combined molar C_{\max} , AUC_{∞} , and AUC_{last} (if it is needed) for TAK-788 and its active metabolites. These ratios will be expressed as a ratio of test treatment relative to the appropriate reference treatment.

Safety:

Quantitative safety data as well as the difference to baseline, when appropriate, will be summarized using the appropriate descriptive statistics.

Sample Size Justification:

The sample size calculation was based on the expected 2-sided 90% CI for the difference in the paired, log-transformed AUC_{∞} means of TAK-788 in the presence and absence of a high-fat meal. The within-patient coefficient of variation for TAK-788 C_{\max} was estimated to be 17.2% on the basis of data from a clinical study conducted in healthy subjects (TAK-788-1001). If the observed GMR for the TAK-788 AUC_{∞} in the presence and absence of high-fat is 1, with a sample size of 12, the 90% CI for the AUC_{∞} GMR is expected to be 0.881 to 1.13 on the basis of the variance assumptions. Fourteen (14) healthy adult subjects will be enrolled into this high-fat meal effect study to get at least 12 PK-evaluable subjects in each treatment arm according to the FDA guidance Assessing the Effects of Food on Drugs in INDs and NDAs – Clinical Pharmacology Considerations Guidance for Industry (FDA FE 2019).

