11.1.3.1 Analysis of Variance

A linear mixed-effects model will be used for the analysis on the ln-transformed C_{max} , AUC_{∞} , and AUC_{last} for TAK-788 and its active metabolites (AP32960 and AP32914). The model will include sequence, treatment, and period as a fixed-effect and subject nested within sequence as a random-effect. Each model will include calculation of LSMs as well as the difference between treatment LSMs.

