11.1.3.2 Ratios and Confidence Intervals

GMR and 90% CI, consistent with the two one sided test [Schuirmann 1987], will be calculated using the exponentiation of the difference between treatment LSMs from the analyses on the ln-transformed C_{max} , AUC_{∞} , and AUC_{last} (if it is needed) for TAK-788 and the combined molar C_{max} , AUC_{∞} , and AUC_{last} (if it is needed) for TAK-788 and its active metabolites. These ratios will be expressed as a ratio of test treatment relative to the appropriate reference treatment.

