#### **Nonparametric Analysis of $t_{max}$**

A nonparametric analysis for  $t_{max}$  will be performed to compare treatment differences using the Wilcoxon Signed Rank test. Median difference (Test-Reference), the Hodges-Lehmann estimator, and estimated confidence interval will be used to examine the location shift in  $t_{max}$ . The  $t_{max}$  parameter will not be ln-transformed. The median difference, associated 95% CI, and p-value will be presented.

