### **7.15 Changes in the Statistical Analysis Plan**

Section 11.1.3.1 of the protocol stated that  $AUC_{last}$  will be included in the ANOVA for TAK-788. However, Section 11.1.3.2 of the protocol stated that  $AUC_{last}$  will be included in the calculation of GMR and 90% CI only if it is needed. The SAP clarified that  $AUC_{last}$  will be included in the ANOVA only if  $AUC_{\infty}$  is not available for at least 12 subjects.

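### The SAP drops the protocol's fed/fasted mixed models for AP32960 and AP32914 Cmax and AUC, and SAP 7.15 does not declare the change

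*SAP*

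**What the plan says.** Protocol 11.1.3.1 (Analysis of Variance) applies a linear mixed model to ln Cmax, AUC∞ and AUClast "for TAK-788 and its active metabolites (AP32960 and AP32914). The model will include sequence, treatment, and period as a fixed-effect". The synopsis repeats the plan and adds "Each model will include calculation of least squares means (LSMs) as well as the difference between treatment LSMs".

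Protocol 11.1.3.2 (Ratios and Confidence Intervals) is narrower. Its geometric mean ratios and 90% intervals cover Cmax, AUC∞ and AUClast ("if it is needed) for TAK-788 and the combined molar" parameters of parent and metabolites). It plans no ratio or interval for either metabolite alone.

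SAP 4.2 keeps the secondary objective, "To assess the PK of active metabolites AP32960 and AP32914 of mobocertinib", and SAP 5.2 keeps metabolite tmax, Cmax, AUC∞ and AUClast as secondary endpoints. SAP 7.10.1 (Food Effect) begins "For evaluation of potential effect of a high-fat meal on mobocertinib PK, a linear mixed-effects model will be used", and that model covers mobocertinib in mass units and the combined molar parameters. AUClast enters only if AUC∞ is unavailable for at least 12 subjects. The individual metabolite parameters are calculated and summarized descriptively by treatment.

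SAP 7.15 declares one change. It begins "Section 11.1.3.1 of the protocol stated that" and goes on to settle when AUClast enters the ANOVA. It describes the protocol ANOVA as being for TAK-788 and leaves the metabolites out.

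**The concern.** Two protocol passages plan a model-based fed/fasted contrast for each metabolite, and the SAP specifies none. SAP 7.15 compares the two protocol sections that differ on this point but resolves only AUClast. A reader cannot tell whether the metabolite models were dropped on purpose or overlooked.

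At stake is the within-subject, period-adjusted contrast for metabolite Cmax and AUC, which is what a crossover provides and by-treatment summaries do not give with any measure of precision. The metabolites are active, AP32960 is a large part of total exposure, and Protocol 4.2 says the study is to support labeling. If the analysis were added after the results were known, it would look post hoc although the protocol planned it.

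**Working it through.** **The passages side by side**

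| Source | Analytes | Parameters | Output |
|---|---|---|---|
| Protocol 11.1.3.1 and synopsis | TAK-788, AP32960, AP32914 | Cmax, AUC∞, AUClast | LSMs and treatment difference |
| Protocol 11.1.3.2 | TAK-788, combined molar sum | Cmax, AUC∞, AUClast if needed | ratio and 90% CI |
| SAP 7.10.1 Food Effect | mobocertinib, combined molar sum | Cmax, AUC∞, AUClast conditionally | LSMs, difference, ratio and 90% CI |

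Read literally, Protocol 11.1.3.1 gives 3 analytes × 3 parameters = 9 models, of which 2 × 3 = 6 are for individual metabolites. The SAP gives 2 × 2 = 4 models plus 2 conditional AUClast models, and none for an individual metabolite.

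**The plan's own figure**

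Protocol 11.2 expects a 90% CI of 0.881 to 1.13 at a ratio of 1, with N = 12 and a within-subject CV of 17.2%.

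- Half-width = t(0.95, 10 df) × √ln(1 + CV²) × √(2/12), with t = 1.812.
- At CV 17.2% this is 0.126, and exp(±0.126) gives 0.881 to 1.135. The figure reproduces.

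It concerns the parent. No within-subject CV is given for the metabolites, so the precision of a metabolite contrast can only be illustrated: a half-width of 0.126, 0.217 or 0.285 on the ln scale for an assumed CV of 17.2%, 30% or 40%.

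**How far the combined sum stands in for a metabolite**

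Protocol 4.1 gives molar AUC24 of AP32960 and AP32914 as about 62% and 8% of parent. Assume that these shares apply to AUC∞, and let the AP32960 share s range from 50% to 75% (also an assumption).

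- Weights at s = 62: parent 100/170 = 0.588, AP32960 62/170 = 0.365, AP32914 8/170 = 0.047. The parent weight is 0.633 at s = 50 and 0.546 at s = 75.
- Combined ratio = (100p + s·a + 8b)/(108 + s), where p, a and b are the fed/fasted ratios of parent, AP32960 and AP32914.
- AP32960 down 30% (a = 0.70, p = b = 1): 151.4/170 = 0.891 at s = 62, 143/158 = 0.905 at s = 50, 160.5/183 = 0.877 at s = 75.
- AP32914 lost entirely (b = 0, p = a = 1): 162/170 = 0.953 at s = 62, 150/158 = 0.949 at s = 50, 175/183 = 0.956 at s = 75.

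The molar AUC∞ metabolite-to-parent ratio in SAP 5.4 is not diluted: in the AP32960 scenario it falls to a/p = 0.70 of its fasted value. It is listed only as a calculated parameter, with no model or interval and no Cmax counterpart. The documents give no molar Cmax shares, so dilution for Cmax cannot be quantified.

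**The case against.** The strongest case is that little is lost and the SAP acted within its authority.

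- **The SAP may modify the plan.** Protocol 11.1 allows this and requires an amendment only for major changes to the primary endpoints or their analysis. This stands: a reader might infer that an amendment was needed, and the documents do not support that. It does not explain why SAP 7.15 is silent.
- **The SAP follows Protocol 11.1.3.2.** Its set of analytes matches that section, and the two protocol sections do not fit together, because 11.1.3.2 uses combined-molar analyses that 11.1.3.1 never lists. Choosing the narrower section is defensible. But 11.1.3.2 names the combined molar parameters explicitly and 11.1.3.1 does not, so the literal reading of 11.1.3.1 as three separate analytes is the stronger one.
- **Only a point estimate was promised.** For each metabolite the protocol plans an LSM difference, not a ratio or interval. With complete data and equal sequences, that difference equals the difference in mean ln values by treatment. With unequal sequences it does not: for an assumed 7 and 5 completers, the raw difference carries (7 − 5)/12 = 1/6 of any period effect. Whether the summaries include geometric means depends on the CPAP.
- **The CPAP may hold the models.** The parameters are those "listed in the CPAP for this study will be determined from the concentration-time profiles for subjects in the PK set", and SAP 7.1 also refers ANOVA presentation to the CPAP. It was not available. The finding is therefore about SAP 7.10.1, where the models are specified, and not about every planning document.
- **The objective is modest.** It is to assess metabolite PK, and descriptive summaries serve it in part. This stands and limits the weight of the point.

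Two stronger readings are tempting. A reader might infer that the combined analysis would miss a metabolite effect because its interval could include 1 while the metabolite's own would not. The documents set no such criterion: Protocol 5.1 states no hypothesis, and the 80–125% range appears only in describing the earlier low-fat study. In the AP32960 scenario at CV 17.2%, the combined lower limit would be exp(ln 0.891 − 0.126) = 0.785, which is hardly unnoticed. A reader might also infer that metabolite tmax is left untested. The SAP's nonparametric analysis "will be performed to compare treatment differences using the Wilcoxon Signed Rank test" names no analyte and may already cover the metabolites, so the point is confined to Cmax and AUC.

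**Conclusion.** The point holds as an undeclared narrowing of a protocol-planned secondary analysis. SAP 7.10.1 specifies no mixed model for Cmax or AUC of AP32960 or AP32914, against six in Protocol 11.1.3.1, and SAP 7.15 does not say so. The primary food-effect analysis is untouched.

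The combined molar sum does not replace the lost contrast. A 30% fall in AP32960 alone would appear there as about 0.89 (0.877 to 0.905), and complete loss of AP32914 as about 0.95 (0.949 to 0.956). These figures are illustrative. They rest on AUC24 shares applied to AUC∞, on an assumed range for the AP32960 share, and on chosen scenarios that no document predicts. They show dilution and nothing about statistical significance.

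This should be fixed because the remedy is cheap and the endpoints are stated ones. It does not threaten the trial's main conclusion.

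**What to change.** In SAP 7.10.1, run the existing PROC MIXED model also on ln Cmax and ln AUC∞ of AP32960 and AP32914 individually, with AUClast only under the SAP's existing 12-subject condition. Report the B − A LSM difference as a secondary result, with the 90% CI that the ESTIMATE statement already produces. The difference restores what Protocol 11.1.3.1 planned. The interval goes beyond Protocol 11.1.3.2 but needs no new code.

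In SAP 7.15, record how Protocol 11.1.3.1 and 11.1.3.2 were reconciled for the metabolites.

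The cost is four model runs (2 metabolites × 2 parameters), a few table rows and a short paragraph. The code takes any PK parameter and the values are already calculated per subject. No further subjects or samples are needed, and Protocol 11.1 requires no amendment for this.
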